2.2 Secondary objectives

- 1. To demonstrate that the change from baseline in ASAS-NSAID score at week 12 is superior for Secukinumab 150 mg s.c. as compared to placebo. To show superiority, both Secukinumab treatment arms will be pooled and compared against placebo.
- 2. To demonstrate that the efficacy of Secukinumab 150 mg s.c at week 12 is superior to placebo based on the change from baseline in the total BASDAI. To show superiority, both Secukinumab treatment arms will be pooled and compared against placebo.
- 3. To demonstrate that the efficacy of Secukinumab 150 mg s.c. (Secukinumab from week 0 with NSAID tapering allowed from week 4; "delayed tapering") at Week 12 is superior to placebo based on the proportion of patients achieving an ASAS20 response.
- 4. To demonstrate that the efficacy of Secukinumab 150 mg s.c. (Secukinumab from week 4 with NSAID tapering allowed from week 4; "early tapering") at Week 12 is superior to placebo based on the proportion of patients achieving an ASAS20 response.
- 5. To demonstrate that the efficacy of Secukinumab 150 mg s.c. (Secukinumab from week 4 with NSAID tapering allowed from week 4; "early tapering") at Week 16 is superior to placebo based on the proportion of patients achieving an ASAS20 response.

- To demonstrate that the change from baseline in ASAS-NSAID score at Week 12 is superior for Secukinumab 150 mg s.c. (Secukinumab from week 0 with NSAID tapering allowed from week 4; "delayed tapering") as compared to placebo.
- 7. To demonstrate that the change from baseline in ASAS-NSAID score at Week 12 is superior for Secukinumab 150 mg s.c. (Secukinumab from week 4 with NSAID tapering allowed from week 4; "early tapering") as compared to placebo.
- 8. To demonstrate that the efficacy of Secukinumab 150 mg s.c. (Secukinumab from week 0 with NSAID tapering allowed from week 4; "delayed tapering") at Week 12 is superior to placebo based on the change from baseline in the total BASDAI.
- 9. To demonstrate that the efficacy of Secukinumab 150 mg s.c. (Secukinumab from week 4 with NSAID tapering allowed from week 4; "early tapering") at Week 12 is superior to placebo based on the change from baseline in the total BASDAI.
- 10. To demonstrate that the efficacy of Secukinumab 150 mg s.c. (Secukinumab from week 4 with NSAID tapering allowed from week 4; "early tapering") at Week 16 is superior to placebo based on the change from baseline in the total BASDAI.

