- 11. To demonstrate that the efficacy of Secukinumab 150 mg s.c. at week 12 is superior to placebo based on the change from baseline in health-related Quality of Life as measured by the SF-36 PCS.
- 12. To demonstrate that the efficacy of Secukinumab 150 mg s.c. (Secukinumab from week 0 with NSAID tapering allowed from week 4; "delayed tapering") at Week 12 is superior to placebo based on the change from baseline in health-related Quality of Life as measured by the SF-36 PCS.
- 13. To demonstrate that the efficacy of Secukinumab 150 mg s.c. (Secukinumab from week 4 with NSAID tapering allowed from week 4; "early tapering") at Week 12 is superior to placebo based on the change from baseline in health-related Quality of Life as measured by the SF-36 PCS.
- 14. To compare between both Secukinumab regimens concerning the change from baseline in ASAS-NSAID score after 12 weeks of Secukinumab exposure (ASAS-NSAID index at Week 12 for "delayed tapering" vs. Week 16 for "early tapering").

2.3 **Exploratory objectives**

- 1. To compare between both Secukinumab regimens concerning the change from baseline in the BASDAI after 12 weeks of Secukinumab exposure (BASDAI at Week 12 for "delayed tapering" vs. Week 16 for "early tapering").
- 2. To evaluate change in patient reported neck, back and hip pain (BASDAI question 2; Appendix 4) beginning from Secukinumab treatment on a continuous basis in patients exposed to Secukinumab 150 mg s.c. for 12 weeks vs. placebo.
- 3. To evaluate change in patient reported neck, back and hip pain (BASDAI question 2; Appendix 4) from baseline on a continuous basis in patients randomized Secukinumab 150 mg s.c. (Secukinumab from week 0 with NSAID tapering allowed from week 4; "delayed tapering") vs. placebo from week 0 to week 12.
- 4. To evaluate change in patient reported neck, back and hip pain (BASDAI question 2; Appendix 4) from baseline on a continuous basis in patients randomized Secukinumab 150 mg s.c. (early tapering) vs. placebo from week 0 to week 16.

Amended Protocol Version v01 Clean

- To compare ASAS20 response rates at week 4 in Secukinumab 150 mg. s.c. (Secukinumab from week 0 with NSAID tapering allowed from week 4; "delayed tapering") vs. week 20 in the patients switching from Placebo after 4 weeks of Secukinumab exposure each.
- 6. Total ASAS-NSAID [Area Under Curve (AUC)] Score from treatment start with Secukinumab to a Secukinumab exposure of 12 weeks.

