3.1 Study design

This is a 20-week, randomized, double-blind, 3-arm, placebo-controlled, parallel-group, multicenter study of Secukinumab (AIN457) to examine the clinical response as measured by the ASAS20 and the NSAID-sparing effect of Secukinumab treatment. The clinical efficacy (ASAS20 response) and the cumulative NSAID sparing effect of two strategies of NSAID tapering after initiation of Secukinumab will be evaluated as compared to placebo:

Patients will be randomized 1:1:1 to one of the following treatment groups:

- Secukinumab delayed NSAID tapering: Secukinumab 150 mg s.c. at weeks 0, 1, 2, 3, 4, 8, 12, 16 and 20 with placebo injections at Week 5, 6, 7 and 17, 18, 19 to maintain the blind.
- **Secukinumab early NSAID tapering:** Placebo at weeks 0, 1, 2, 3 to maintain the blind; followed by Secukinumab 150 mg s.c. at Week 4, 5, 6, 7, 8, 12, 16 and 20 with intermittent Placebo injections at week 17, 18, 19 to maintain the blind.
- **Placebo:** Placebo at weeks 0, 1, 2, 3, 4, 5, 6, 7, 8 and 12. After the Week 16 assessments of the secondary endpoint have been performed, these patients will receive Secukinumab 150 mg s.c. at weeks 16, 17, 18, 19 and 20.

The patients will be stratified at randomization according to their status of prior TNF α inhibitor exposure, i.e. TNF α inhibitor naive patients or TNF α inhibitor inadequate responders (TNF α -IR). The only condition that will be placed on enrollment targets for each stratum is that no less than 60% of patients (122 patients) are TNF α inhibitor naïve, i.e., no more than 40% of patients (82 patients) are TNF α -IR. In theory the percentage of TNF α inhibitor naïve patients could reach 100%, although that is not anticipated.

All patients will be advised to continue on the maximum recommended/tolerated dose of NSAIDs for the first 4 weeks of the trial.

A follow-up visit is to be done 4 weeks after last study treatment administration for all subjects, regardless of whether they complete the entire study as planned or discontinue prematurely.

NSAID tapering strategy

All patients will be advised to taper/discontinue their NSAID intake starting at Week 4 to Week 20. Patients may use NSAIDs on an on-demand basis to avoid an unacceptable worsening of disease activity.

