	secukinumab 150 mg s.c. (early tapering) vs. placebo.
To evaluate change in patient reported neck, back and hip pain (BASDAI question 2; Appendix 4) from baseline on a continuous basis in patients randomized Secukinumab 150 mg s.c. (Secukinumab from week 0 with NSAID tapering allowed from week 4; “delayed tapering”) vs. placebo from week 0 to week 12.	Mean change in patient reported neck, back and hip pain score (BASDAI question 2) from baseline for secukinumab 150 mg s.c. (delayed tapering) vs. placebo from baseline (week 0) to week 12.
To evaluate change in patient reported neck, back and hip pain (BASDAI question 2; Appendix 4) from baseline on a continuous basis in patients randomized Secukinumab 150 mg s.c. (early tapering) vs. placebo from week 0 to week 16.	Mean change in patient reported neck, back and hip pain score from baseline for secukinumab 150 mg s.c. (early tapering) vs. placebo from week 0 to week 16.
To compare ASAS20 response rates at week 4 in Secukinumab 150 mg. s.c. (Secukinumab from week 0 with NSAID tapering allowed from week 4; “delayed tapering”) vs. week 20 in the patients switching from Placebo after 4 weeks of Secukinumab exposure each.	Proportion of patients fulfilling ASAS20 criteria at week 4 for secukinumab 150 mg s.c. (delayed tapering) vs. week 20 in patients switching from placebo after weeks of secukinumab exposure.
To explore the total ASAS-NSAID [Area Under Curve (AUC)] Score from treatment start with Secukinumab to a Secukinumab exposure of 12 weeks.	Total ASAS-NSAID [Area Under Curve (AUC)] Score for both secukinumab arms from week 0 to week 12 for secukinumab 150 mg s.c. (delayed tapering) and from week 0 to week 16 for secukinumab 150 mg s.c. (early tapering).
To explore the total ASAS-NSAID [Area Under Curve (AUC)] Score from Week 4 to Week 16 for each treatment arm.	Total ASAS-NSAID [Area Under Curve (AUC)] Score for each treatment arm from Week 4 to Week 16.
To explore the efficacy of secukinumab based on the proportion of patients with no NSAID intake after Secukinumab exposure of 12 weeks.	Proportion of patients with no NSAID intake at week 12 for secukinumab 150 mg s.c. (delayed tapering) and at week 16 for secukinumab 150 mg s.c. (early tapering).
To explore the efficacy of Secukinumab 150 mg s.c. in patients with no NSAID intake at week 12.	Proportion of patients with no NSAID intake at week 12 for each treatment arm.

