##### **2.7.1 Secondary endpoints**

The secondary efficacy variables are listed below. Secondary efficacy variables will be analyzed using the FAS population.

- ASAS20 response at Week 12/16.
- ASAS-NSAID response at Week 12.
- Change from baseline in BASDAI at Week 12/16.
- Change from baseline in SF36 physical component score at Week 12/16.
- Change from baseline in ASAS-NSAID score at Week 12 for Secukinumab (delayed tapering) vs. change from baseline in ASAS-NSAID score at Week 16 for Secukinumab (early tapering)
- Change from baseline in BASDAI at Week 12 for Secukinumab (delayed tapering) vs change from baseline in BASDAI at Week 16 for Secukinumab (early tapering).
- Change from baseline in BASDAI question 2
- ASAS20 response at Week 4 for Secukinumab (delayed tapering) vs. ASAS20 response at Week 20 for placebo group

Please refer to the main definition section.

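### The early-versus-delayed NSAID comparison matches secukinumab exposure but sets 8 weeks of allowed tapering against 12, and the equal-window NSAID results are only descriptive

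*Protocol*

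**What the plan says.** Protocol 3.1 holds NSAIDs first: "All patients will be advised to continue on the maximum recommended/tolerated dose of NSAIDs for the first 4 weeks of the trial". Then: "All patients will be advised to taper/discontinue their NSAID intake starting at Week 4 to Week 20". The two secukinumab regimens therefore differ in when the drug starts, not in when tapering opens. Protocol 2.2 describes delayed tapering as "Secukinumab from week 0 with NSAID tapering allowed from week 4" and early tapering as "Secukinumab from week 4 with NSAID tapering allowed from week 4".

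Secondary objective 14 reads "To compare between both Secukinumab regimens concerning the change from baseline in ASAS-NSAID score after 12 weeks of Secukinumab exposure", with Week 12 for the delayed regimen and Week 16 for the early one. SAP 2.7.1 lists it as "Change from baseline in ASAS-NSAID score at Week 12 for Secukinumab (delayed tapering) vs. change from baseline in ASAS-NSAID score at Week 16" for the early regimen. Exploratory objectives 1 (BASDAI) and 26 (all other endpoints) use the same pair of visits. Objective 26 gives the reason: both arms have then had 12 weeks of secukinumab.

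Two NSAID endpoints are planned by arm over a common calendar window: ASAS-NSAID AUC from Week 4 to Week 16, and the proportion with no NSAID intake at Week 12 (Protocol 2.3, objectives 7 and 9; SAP Table 1.2-1). SAP 2.13 says that exploratory endpoints are summarised descriptively. For ASAS-NSAID, SAP 2.7.2 specifies the pooled contrast and the pairwise comparisons with placebo, and no early-versus-delayed contrast at the same visit.

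Protocol 2.3, objective 6, and SAP 2.13, item 1, run another ASAS-NSAID AUC from the start of secukinumab to 12 weeks of exposure. SAP Table 1.2-1 instead gives the windows as "from week 0 to week 12 for secukinumab 150 mg s.c. (delayed tapering) and from week 0 to week 16" for early tapering.

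**The concern.** ASAS-NSAID change measures how far a patient has tapered. Comparing one arm after 8 weeks of permitted tapering with another after 12 mixes the effect of the regimen with four extra weeks in which intake can fall. Any resulting gap favours the early regimen. The contrast also compares randomised arms at different calendar visits, although concurrent data exist at both visits.

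Protocol 1.2 hopes that the results may guide how NSAIDs are adjusted after secukinumab is started. A lower score for the early regimen at Week 16 than for the delayed regimen at Week 12 could be read as evidence for early tapering when it reflects only more time. No inferential contrast is specified that would let a reader tell the two apart.

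**Working it through.** **Inputs.** Assumed reduction 63.9 points (placebo 36.6) and SD 40: Protocol 9.7. Allocation 1:1:1 and about 190 patients, hence about 63 per arm: SAP 1.1. Two-sided 5%: SAP 2.1. Tapering from Week 4: Protocol 3.1. The documents give no taper curve, so the curves below are assumptions.

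**The plan's own figure.** Each secukinumab arm versus placebo: difference 63.9 − 36.6 = 27.3; with 62 per arm, SE = 40·√(2/62) = 7.18; power = Φ(27.3/7.18 − 1.96) = 96.7%. This agrees with the stated figure of more than 90%. No power is stated for early versus delayed.

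**Allowed tapering time.** Delayed at Week 12: 12 − 4 = 8 weeks. Early at Week 16: 16 − 4 = 12 weeks.

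**Identical tapering in both arms.** Let R(t) be the reduction after t weeks of tapering. The artefact is R(12) − R(8). With 63 per arm, SE = 40·√(2/63) = 7.13, so about 14.0 points reaches p < 0.05. The chance of a significant result favouring early is Φ(gap/7.13 − 1.96).

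| Assumed taper (63.9-point end value or plateau) | R(12) − R(8), visit-day score | Chance of significance favouring early |
|---|---|---|
| Linear, complete by 8 weeks | 63.9 − 63.9 = 0 | 2.5% |
| Exponential, half-life 2 weeks | 63.9·(2⁻⁴ − 2⁻⁶) = 3.0 | 6% |
| Exponential, half-life 4 weeks | 63.9·(2⁻² − 2⁻³) = 8.0 | 20% |
| Exponential, half-life 6 weeks | 63.9·(2^(−4/3) − 2⁻²) = 9.4 | 26% |
| Linear over 10 weeks | 63.9 − 51.1 = 12.8 | 43% |
| Linear over 12 weeks | 63.9 − 42.6 = 21.3 | 85% |

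In a same-visit contrast (Week 12 or Week 16), the same identical tapering gives a gap of 0 and the nominal 2.5%.

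**Sensitivity to how the score is built.** SAP 5.5.7 scores intake over a period of interest but does not define that period for the Week 12 and Week 16 scores. If it is the time since the previous visit (Weeks 8–12 versus 12–16), the linear taper complete at 8 weeks gives 63.9 − 47.9 = 16.0 points (61%), the 2-week half-life 6.5 points (15%), the 10-week linear taper 22.4 points (88%) and the 12-week linear taper 21.3 points (85%). A taper complete in one week still gives 0.

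**AUC windows.** Take the 12-week linear taper in both arms and a baseline score B. The cumulative reduction is (63.9/12)·8²/2 = 170.4 score-weeks over 8 weeks of tapering and (63.9/12)·12²/2 = 383.4 over 12.

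- Protocol windows (Weeks 0–12 delayed, 4–16 early): intake 12B − 170.4 versus 12B − 383.4, so early is lower by 213.0. The lengths are equal, but only the delayed window contains the four-week NSAID hold.
- SAP Table 1.2-1 windows (Weeks 0–12 delayed, 0–16 early): 12B − 170.4 versus 16B − 383.4, so early is higher by 4B − 213.0. That is 42.6 at B = 63.9 (the lowest B that allows a 63.9-point reduction) and 187.0 at B = 100. The excess is simply the early arm's intake in Weeks 12–16, which cannot be negative.
- Weeks 4–16 in both arms: difference 0.

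**The case against.** The strongest defence is that exposure matching is deliberate and answers a sensible question: 12 weeks after starting secukinumab, how much NSAID has been spared if tapering began at once or four weeks later? On that view, the extra tapering time belongs to the early strategy. No visit pair equalises both clocks: at Week 12, tapering is 8 versus 8 weeks but exposure is 12 (delayed) versus 8 (early). This stands, and it is why objective 14 should remain. It does not make the contrast interpretable alone as a difference between regimens.

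The size can also be challenged. The NSAID hypotheses H2, H7 and H8 are tested at Week 12. If 63.9 points is the reduction expected after 8 weeks of tapering, a linear taper would reach 63.9 × 12/8 = 95.9 by Week 16 on a score normally between 0 and 100, with entry allowed from half the maximum dose. Flattening is then more plausible and the visit-day artefact may be small or nil. Identical calendar tapering is itself a reference case, because tapering follows pain and the early arm starts the drug later. A reader might infer from the 85% that a false result is likely; the documents give no taper curve to support that.

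A reader might also infer that no other comparison of NSAID use by regimen is planned. That is not so. The Week 4–16 AUC and the no-intake proportion at Week 12 are planned by arm, and SAP 2.13 plots the score over time. Protocol 9.5.1 allows, for continuous variables generally, pairwise comparisons with secukinumab as well as placebo at the appropriate visits, and the mixed-model code in SAP 5.4 would output them. What is missing is a specified same-visit contrast with an interval.

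Finally, objective 14 lies outside H1 to H11, so no confirmatory claim or error rate is affected.

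**Conclusion.** The point holds in a limited form. Objective 14, like every head-to-head regimen contrast named by visit, sets Week 12 against Week 16, which means 8 versus 12 weeks of allowed tapering. It can favour early tapering without any regimen effect, provided that intake, or the average that is scored, is still falling after 8 weeks of tapering. Under the assumed curves, the visit-day artefact is 0 to 21.3 points and the chance of a significant result favouring early is 2.5% to 85%. These figures rest on identical tapering, 63 per arm, SD 40, a 63.9-point reduction or plateau and no covariate adjustment. Equal-window NSAID results are planned, but only descriptively.

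The AUC window in SAP Table 1.2-1 is a separate defect. It conflicts with the protocol and with SAP 2.13, while SAP section 4 reports no change from the protocol. A reader might take it as a second bias towards early tapering; it works the other way, since the extra four weeks add to the early arm's total intake.

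Nor do the documents support demoting the exposure-matched contrast or extending the argument to BASDAI, which measures disease activity rather than tapering.

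**What to change.** Keep objective 14 as the exposure-matched contrast, and make these additions:

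- In SAP 2.7.2, specify early-minus-delayed contrasts in ASAS-NSAID change at Week 12 and at Week 16 from the existing MMRM, with 95% CIs.
- In SAP 2.13, report the early-minus-delayed difference in ASAS-NSAID AUC over Weeks 4 to 16 with a 95% CI, not only summaries by arm.
- State beside the results that objective 14 mixes regimen with four extra weeks of tapering, and that the same-visit contrasts differ by four weeks of drug exposure.
- In SAP Table 1.2-1, correct the exposure-based AUC to equal 12-week windows consistent with the protocol (Weeks 0–12 delayed, 4–16 early). Note that only the delayed window includes the NSAID hold, so this AUC shares objective 14's limitation.
- In SAP 5.5.7, define the period of interest behind the Week 12 and Week 16 scores, since it changes the size of the artefact.

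BASDAI needs no change. The treatment-by-visit differences with confidence limits already come out of the model code in SAP 5.4, so the contrasts need no new model. The AUC difference is one further estimate. The hierarchy H1 to H11 and its alpha are untouched. The SAP's document history is marked as before database lock, so the additions can be prespecified if lock has not yet taken place.

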3.1 Study design

This is a 20-week, randomized, double-blind, 3-arm, placebo-controlled, parallel-group, multicenter study of Secukinumab (AIN457) to examine the clinical response as measured by the ASAS20 and the NSAID-sparing effect of Secukinumab treatment. The clinical efficacy (ASAS20 response) and the cumulative NSAID sparing effect of two strategies of NSAID tapering after initiation of Secukinumab will be evaluated as compared to placebo:

Patients will be randomized 1:1:1 to one of the following treatment groups:

- Secukinumab delayed NSAID tapering: Secukinumab 150 mg s.c. at weeks 0, 1, 2, 3, 4, 8, 12, 16 and 20 with placebo injections at Week 5, 6, 7 and 17, 18, 19 to maintain the blind.
- **Secukinumab early NSAID tapering:** Placebo at weeks 0, 1, 2, 3 to maintain the blind; followed by Secukinumab 150 mg s.c. at Week 4, 5, 6, 7, 8, 12, 16 and 20 with intermittent Placebo injections at week 17, 18, 19 to maintain the blind.
- **Placebo:** Placebo at weeks 0, 1, 2, 3, 4, 5, 6, 7, 8 and 12. After the Week 16 assessments of the secondary endpoint have been performed, these patients will receive Secukinumab 150 mg s.c. at weeks 16, 17, 18, 19 and 20.

The patients will be stratified at randomization according to their status of prior TNF α inhibitor exposure, i.e. TNF α inhibitor naive patients or TNF α inhibitor inadequate responders (TNF α -IR). The only condition that will be placed on enrollment targets for each stratum is that no less than 60% of patients (122 patients) are TNF α inhibitor naïve, i.e., no more than 40% of patients (82 patients) are TNF α -IR. In theory the percentage of TNF α inhibitor naïve patients could reach 100%, although that is not anticipated.

All patients will be advised to continue on the maximum recommended/tolerated dose of NSAIDs for the first 4 weeks of the trial.

A follow-up visit is to be done 4 weeks after last study treatment administration for all subjects, regardless of whether they complete the entire study as planned or discontinue prematurely.

NSAID tapering strategy

All patients will be advised to taper/discontinue their NSAID intake starting at Week 4 to Week 20. Patients may use NSAIDs on an on-demand basis to avoid an unacceptable worsening of disease activity.

From Week 16 on, those patients originally randomized to placebo will self-inject Secukinumab 150 mg at weeks 17, 18, 19 and 20, while patients originally randomized to either of the Secukinumab groups will receive their next Secukinumab injection after Week 16 at Week 20 with Placebo injections at weeks 17, 18, 19 to maintain the blinding of the treatment assignment for the secondary / exploratory endpoint analyses.

Patients will be asked to capture NSAID intake and level of AS neck, back and hip pain (BASDAI question 2; see Appendix 4) on a daily basis in a patient diary. Guidance will be

provided to patients that NSAID intake should be reduced upon an improvement in back pain and that the reduction should preferably happen step-wise and instead of an abrupt stop of any NSAID intake. However, deviance from this guidance will be acceptable and may be discussed between investigator and patient. Patients may deviate from this guidance if required, e.g. NSAID use necessary for non-spinal pain (e.g. entheses, peripheral joints, and headache). Also, if pain levels increase, patients may increase NSAID usage on an on-demand basis. The reduction in NSAID intake will be assessed using the ASAS-NSAID score (Dougados et al 2012).

